RESEARCH PROTOCOL TEMPLATE
INVESTIGATOR INITIATED TREATMENT TRIALS

Title of Project: A Randomized, Controlled, Double-Blind Trial of 3 Local Anesthetics for Spinal Anesthesia in Primary Total Hip Arthroplasty

Principal Investigator: [name]; MD; TJUH Anesthesiology

Co-Investigators: [name]; MD; TJUH Anesthesiology
[name]; MD; TJUH Anesthesiology
[name]; MD; TJUH Anesthesiology
[name]; MD; TJUH Anesthesiology
[name]; MD; TJUH Anesthesiology
[name]; MD; TJUH Anesthesiology
[name]; DO; TJUH Anesthesiology
[name]; TJUH Anesthesiology
[name]; TJUH Anesthesiology
[name]; MD; TJUH Orthopedic Surgery
[name]; MD; TJUH Orthopedic Surgery
[name]; MD; TJUH Orthopedic Surgery
[name]; United Anesthesia Partners
[name], DPT
[name], DPT
[name], DPT
[name], DPT

NCT number: NCT03948386

Abstract

Hip replacements are commonly performed under spinal anesthesia. Compared to general anesthesia, spinal anesthesia may reduce operative time, cardiopulmonary complications, and the need for blood transfusion.¹ Spinal anesthesia may also allow for earlier ambulation in the postoperative period. Ambulation is encouraged after hip surgery, as delays have been associated with delirium, pneumonia, and increased length of stay.² Early ambulation may also lead to better functional recovery.³ Several spinal local anesthetics exist, each with its own unique pharmacologic properties. In this prospective randomized trial, we will determine if a short-acting spinal medication, mepivacaine, leads to earlier postoperative ambulation following primary hip replacement surgery compared to two other formulations of another long-acting spinal local anesthetic, bupivacaine.

Note: The Research Plan, A through E, should not exceed 4 pages.

A. Specific Aims

State the hypothesis and specific aims. List the long-term objectives and what

the proposed research will accomplish. (Suggested length: a paragraph or two)

The specific aims of this study are to compare isobaric bupivacaine, hyperbaric bupivacaine, and isobaric mepivacaine as spinal anesthetic agents in the following areas:

1. Percentage of patients ambulating at 3 hours (primary outcome)
2. Return of sensory and motor function of lower extremities, incidence of hypotension, urinary retention, transient neurological symptoms (TNS)
3. Postoperative pain levels, opioid consumption, percentage of patients able to meet discharge criteria on same day, length of stay

Hypothesis: we hypothesize that a greater percentage of patients will ambulate early in the mepivacaine group compared to the two bupivacaine groups and that the smallest percentage of patients will ambulate early in the isobaric bupivacaine group.

B. Background and Significance

Mepivacaine has a shorter duration of action than bupivacaine. Although some early studies suggested that mepivacaine might cause temporary pain in the buttocks and thighs, also known as transient neurological symptoms (TNS), mepivacaine has been utilized safely as a spinal anesthetic⁴ and more recent studies have refuted that.⁵ Mepivacaine spinal anesthesia has been shown in retrospective studies to facilitate rapid recovery in total knee arthroplasty compared to hyperbaric bupivacaine⁵ but this study was limited because the time of evaluation was not controlled and differences in ambulation may have been missed as a result. Both hyperbaric and isobaric bupivacaine provide reliable anesthesia for a variety of surgeries and there appears to be no difference in the failure rate of the two drugs.⁶ Even when used in low doses, both provide adequate anesthesia for greater than 60 minutes, which is the expected surgical time for this study. We will be using “low-dose” bupivacaine for both bupivacaine groups in an effort to maximize chance of early ambulation. Early ambulation is known to facilitate better functional recovery and reduce the incidence of some postoperative complications after hip surgery. A shorter-acting spinal anesthetic like mepivacaine may facilitate earlier ambulation in the postoperative period after hip surgery. Shorter time to ambulation could lead to faster discharge, which is desirable by both patients and surgeons and could reduce healthcare costs.

C. Preliminary Studies/Progress Report

Existing evidence is limited by its retrospective nature⁵ and the inherent confounders and lack of controlling that were present. A review comparing isobaric to hyperbaric bupivacaine found that both drugs provide safe anesthesia but that isobaric bupivacaine has a slower onset and longer duration.⁶ A prospective, randomized trial comparing two doses of isobaric mepivacaine for ambulatory surgery found that both groups of patients were suitable for same-

Postoperatively, patient sensory and motor assessments will occur every 30 minutes until strength returns to 5/5 in hip flexion, knee extension, and toe dorsiflexion. The sensory dermatome where numbness is detected at that time will be noted. Patients will be asked on POD 0, 1, and 2 about presence of TNS as defined above: **“Do you have any back pain that you didn’t have before surgery that goes into your buttocks, thighs, hips, or lower leg?”**

Urinary retention will be defined by inability to urinate within 8 hours OR a report of distended or painful bladder occurring on POD 0, either by patient report or on palpation by nursing.

90-day readmissions will be queried in Epic.

E. Statistical Methods

If not a pilot study, provide biostatistical design, power calculations determining the number of participants, and the proposed analysis. (suggested length: ½ page)

The study was powered using estimates of the study’s primary endpoint which is the percent of patients successfully ambulating within a 3-hour window post-surgery. The time window is based on realistic expectations of when Physical Therapy assessments will be performed with a near 0 percent chance of missing first ambulation. The assumptions are also supported by available data in the literature on duration of spinal blocks as well as our clinical experience and time to postoperative ambulation for these surgical procedures. We believe that it is reasonable to expect ambulation within 3 hrs in 70% of patients for mepivacaine, 35% of patients for hyperbaric bupivacaine, and 25% of patients for isobaric bupivacaine. With a one-way ANOVA for 3 groups and alpha set at 0.05, the study will require 44 patients per group (N=132) to achieve 80% power to detect a statistically significant difference between the 3 groups in the percent of patients ambulating within 3 hours. Allowing for a 10% dropout and screen failure rate the study will require a total of 144 patients.

F. Gender/Minority/Pediatric Inclusion for Research

All protocols must include documentation of the inclusion of women and minorities in the research protocol. If women and minorities are not to be included, provide rationale for exclusion.

Women and minorities will be included in this research protocol.

G. Human Subjects

1. Provide number, age range, and health status of the subject population. List criteria for inclusion or exclusion.

This study will include 144 subjects. Patients between the ages of 18 and 85 will be included. ASA physical status 1, 2, and 3 will be included. Patients who have a contraindication to spinal anesthesia will be excluded as will patients with body mass index (BMI) greater or equal to 40 kg/m². Patients with pre-existing neuropathy in the lower extremities will also be excluded and any patient deemed a poor study candidate by the attending anesthesiologist will be excluded at his or her discretion. Patients in wheelchairs and those who cannot ambulate 25 feet with or without an assist device will be excluded. Those who take greater than the equivalent of 25 mg IV morphine (oxycodone 30 mg) daily will be excluded.

2. Identify sources of research material in the form of specimens, records or data.

All data will be from interviewing patients before and after surgery and from review of Epic record (TJUH) or Meditech record and paper records (ROSH) from their admission. Rothman databases may be accessed if data are missing from Epic.

3. Describe plans for recruitment and consent procedures to be followed.

As described above, patients will be called the night before surgery to discuss purpose of study and determine if further steps and official consent should take place on the day of surgery. Patients expressing interest by phone and those who are not able to be contacted by phone but are eligible will be approached on the day of surgery to discuss the purpose, risks and benefits, and any questions. If available, family members will be involved in consent process as well.

4. Describe risks and assess likelihood and seriousness.

One risk of the study is premature resolution of spinal block necessitating general anesthesia conversion (unlikely and moderate severity). The other main risk is that early ambulation could put patients at risk for falls, although this risk is minimized by having the physical therapist walk with the patient during this session and patients without adequate resolution of spinal level would not attempt ambulation at that time.

5. Describe procedures for protecting against or minimizing potential risks.

Only patients who are undergoing primary unilateral hip arthroplasty with one of 3 surgeons with typical operating times of 60 minutes or less will be candidates. This minimizes risk of patients being enrolled whose surgeries

would outlast the spinal duration. The risk of falls is minimized by physical therapists walking with the patients.

6. Describe potential benefits and importance to the subjects and others.
Patients who receive mepivacaine spinal anesthesia may be able to ambulate sooner after surgery. Early ambulation could theoretically lead to decreased hospital length of stay. A shorter duration of spinal anesthesia may also lead to less urinary retention and systemic hypotension.
7. Discuss why risks are reasonable in relation to benefits.
There is always a risk of conversion to general anesthesia when spinal anesthesia is used. That risk may be greater in this study because low doses of bupivacaine are used or mepivacaine is used. However, data from existing studies as well as our clinical experience suggest that with the three surgeons in this study this risk should be low. This is weighed against the moderate to good probability that patients may ambulate sooner and therefore have a chance at earlier discharge, which would be a benefit.

H. Data and Safety Monitoring Plan

All protocols that pose greater than minimal risk must have a Data and Safety Monitoring Plan (see DHSP policy G 616 "Independent Monitoring of Investigator-Initiated Clinical Trials."

[name] will be the independent study monitor. Quarterly meetings in person or via telephone with the PI will take place and adverse events will be discussed. Any event determined to be severe will be addressed immediately.

1. Describe the Data and Safety Monitoring Plan (DSMP)
 - a. reporting mechanisms for adverse events to the IRB, FDA, and NIH.
 - b. adverse event (AE) grading
 - c. plan for unanticipated AE reporting
 - d. plan for annual reporting of AEs
 - e. interim efficacy analysis where appropriate
2. If applicable, describe the Data and Safety Monitoring Board (DSMB) that will be responsible for monitoring the study. Indicate Chair, members, areas of expertise, frequency of meetings, distribution of reports.

N/A

I. Literature Cited

List only literature cited within the text. (suggested length: no more than 12 references)

1. Basques BA, et al. General Compared with Spinal Anesthesia for Total Hip Arthroplasty. J Bone Joint Surg Am 2015; 97(6): 455-61.

2. Kamel HK, et al. Time to Ambulation After Hip Fracture Surgery: Relation to Hospitalization Outcomes. *J Gerontol A Biol Sci Med Sci* 2003; 58(11): 1042-5.

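### Section E names only a three-group omnibus test, which does not test the stated hypothesis; the pairwise tests, alpha handling and claim rule need to be written down

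*Combined protocol and SAP*

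**What the plan says.** Section A (Specific Aims) ends with a directional hypothesis in two parts. The first is that "a greater percentage of patients will ambulate early in the mepivacaine group compared to the two bupivacaine groups". The second is that the "smallest percentage of patients will ambulate early in the isobaric bupivacaine group". The Abstract asks the first part as the trial's question: whether mepivacaine "leads to earlier postoperative ambulation following primary hip replacement surgery compared to two other formulations" of bupivacaine.

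Section E (Statistical Methods) gives planning rates of "70% of patients for mepivacaine, 35% of patients for hyperbaric bupivacaine, and 25% of patients for isobaric bupivacaine". It names one method, inside the sample-size sentence: "With a one-way ANOVA for 3 groups and alpha set at 0.05". The power is for a global difference: "the study will require 44 patients per group (N=132) to achieve 80% power to detect a statistically significant difference between the 3 groups".

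The template prompt at the head of Section E asks the authors to "provide biostatistical design, power calculations determining the number of participants, and the proposed analysis". The first two items are answered. No analysis is described beyond the power sentence, and no other section names a test, a sidedness, an order of testing or an adjustment for several comparisons.

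**The concern.** A significant three-group test rejects equality of the three rates. It does not say which arm differs, or in which direction. It would be significant, for example, if mepivacaine were clearly better than isobaric bupivacaine and no better than hyperbaric, which is not what Section A predicts. The stated test therefore settles neither part of the hypothesis.

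The step from the omnibus result to a statement about mepivacaine is left open and could be chosen after the data are seen. The choice matters for power: among rules that test both mepivacaine contrasts, the chance of success at the planning rates runs from 81% to 96%. It also matters for error. If all three pairs were tested at 0.05 with no gate and any win were claimed, the familywise error under equal rates would be about 12–13%.

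The phrase about the two bupivacaine groups is itself open. It can mean each group separately, the reading used here, or both pooled. The plan should say which.

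**Working it through.** **Inputs.** Rates 0.70, 0.35 and 0.25, 44 per group, alpha 0.05 (all Section E). Two-sided testing is my assumption, because the plan gives no sidedness. Equal allocation is inferred from 44 per group.

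**1. The plan's own figure: 80% omnibus power at 44 per group.**
- Mean rate = (0.70 + 0.35 + 0.25)/3 = 0.4333.
- Between-group variance = (0.2667² + 0.0833² + 0.1833²)/3 = 0.0372.
- Mean within-group variance = (0.2100 + 0.2275 + 0.1875)/3 = 0.2083.
- Effect size f = √(0.0372/0.2083) = 0.423. With the total variance, 0.4333 × 0.5667 = 0.2456, f = 0.389.
- Noncentral F power at 44 per group is 99.4% (within-group variance) or 98.3% (total variance). A 2-df chi-square gives 98.5%.
- 80% power needs 20 to 23 per group across these variants and the arcsine scale.
- For 44 per group to give 80%, f would have to be 0.273, which the stated rates do not produce.

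The stated 80% therefore does not reproduce.

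**2. Power of each pair at 44 per arm.** Normal approximation: power = Φ{[d√n − 1.96√(2p̄(1−p̄))] / √(p₁(1−p₁) + p₂(1−p₂))}, where d is the difference and p̄ the mean of the two rates.
- Mepivacaine vs hyperbaric: (0.35 × 6.633 − 1.96 × 0.7062)/0.6614 = 1.417, so 92.2%.
- Mepivacaine vs isobaric: (0.45 × 6.633 − 1.96 × 0.7062)/0.6305 = 2.539, so 99.4%.
- Hyperbaric vs isobaric: (0.10 × 6.633 − 1.96 × 0.6481)/0.6442 = −0.942, so 17.3%.

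**3. Joint results.** Exact enumeration of all 45³ = 91,125 outcomes, uncorrected Pearson chi-square tests:

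| Event at 70/35/25%, 44 per arm | Probability |
|---|---|
| Omnibus significant (chi-square; ANOVA F on 0/1 data the same) | 99.0% |
| Mepivacaine above hyperbaric | 91.3% |
| Mepivacaine above isobaric | 99.2% |
| Mepivacaine above both, no gate | 90.9% |
| Mepivacaine above both, after a significant omnibus | 90.9% |
| Omnibus significant, but not above both | 8.1% |
| Above both, one-sided 0.05 each | 96.1% |
| Above both, Bonferroni over three pairs | 81.0% |
| Hyperbaric vs isobaric significant | 18.2% |

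Of the 8.1%, 7.8 points are trials in which mepivacaine is significantly above isobaric only. If all 48 per arm (144/3) are evaluable, power for both contrasts is 94%.

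**4. Error control with the gate.** If all three rates are equal, no pair is tested unless the omnibus rejects. Its simulated error was 5.0% at common rates of 25%, 35% and 43%. If only two rates are equal, one true null pair remains, tested at 0.05. Familywise error is therefore about 0.05 without splitting alpha. This argument holds for exactly three groups.

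**5. Isobaric lowest.** Beyond the mepivacaine contrasts, this needs hyperbaric above isobaric. The 95% CI half-width is 1.96 × √(0.2275/44 + 0.1875/44) = 0.190, around an expected difference of 0.10. For 80% power, n = [1.96√0.42 + 0.8416√0.415]²/0.10² = 328.5, so 329 per arm.

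**6. Other rates (assumed, not in the documents).**
- Hyperbaric 50%, others as planned: omnibus 98.2%, both mepivacaine contrasts 49.2%.
- Mepivacaine 50%, others as planned: omnibus 59.1%, both contrasts 25.7% (25.4% with the gate).
- Mepivacaine against the two bupivacaine arms pooled: 99.5% at the planning rates and 95.8% with hyperbaric at 50%. The each-or-pooled question is therefore not a formality.

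**The case against.** The strongest reply is that pairwise testing after a significant omnibus result is customary, that with three groups it controls familywise error, and that the mepivacaine contrasts are well powered at 44 per arm even with Bonferroni (81.0%). All of that stands. It limits the seriousness of the point and shows that the named test need not be discarded. It does not close the gap, because the plan states neither the procedure nor what would count as support for the hypothesis.

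It is also fair that Section E claims no power for hyperbaric against isobaric, so 18% contradicts no stated figure. That part concerns what readers should be told.

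Two stronger readings are tempting:
- A reader might infer that the investigators mean to treat a significant omnibus test as proof of the mepivacaine claim, or a ranking of point estimates as proof that isobaric is lowest. No section says either. The 99% is the power of the omnibus test, not the chance of a mepivacaine claim under any stated rule.
- A reader might infer that the 44 came from an undisclosed pairwise calculation. Mepivacaine against hyperbaric does need 42 per group at 0.05/3, or 43 at 0.05/2 with continuity correction. These are near matches only, and the document does not say that either was used.

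**Conclusion.** The point holds as an omission that should be corrected, with high confidence. The one test named cannot establish either part of the Section A hypothesis, and no rule connects it to a claim.

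It would be too strong to conclude that the trial cannot answer its question or that the omnibus test must be replaced. With two-sided 0.05 tests and the hypothesis read as mepivacaine above each arm, power for both contrasts is about 91% at the planning rates, above the planned 80%, with or without the gate. Nor is adequate power guaranteed: it rests on those rates and drops to about half or a quarter under the assumed alternatives in the working.

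The isobaric-lowest part is not realistically testable at this size. Separately, the stated 80% omnibus power disagrees with the plan's own inputs, which give about 99%, and should be reconciled in the same revision.

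**What to change.** Add an analysis paragraph to Section E. Suggested wording:

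> The three groups will be compared on the primary endpoint at the 0.05 level. If this test is significant, each pair of groups will be compared by a two-sided 0.05 test of proportions. The mepivacaine hypothesis will be claimed in full only if mepivacaine is significantly higher than both hyperbaric and isobaric bupivacaine. A significant difference from one group will be reported as a result for that group only. Hyperbaric versus isobaric bupivacaine is a secondary comparison, reported as a risk difference with a 95% confidence interval. Its power is about 18% at the planning rates, and the ranking of the observed percentages alone will not be taken as evidence that isobaric bupivacaine is lowest.

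A rule without the gate, under which mepivacaine must beat both arms at two-sided 0.05, is an acceptable alternative with the same power. Whether a win over one arm deserves its own claim is for the investigators to decide, before unblinding.

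Also state in Section A whether the comparison is with each bupivacaine group or with both pooled. If pooled is meant, the claim rule above must change. Restate the power for the contrasts that carry the claim, and correct or explain the 80%.

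The cost is a few sentences and no added patients. The stated power for the mepivacaine claim becomes about 91%, below the computed omnibus figure of about 99%, and the isobaric-lowest statement becomes softer.

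### The stated 44 per group for 80% power does not follow from the stated inputs: the one-way ANOVA on 70/35/25% needs about 20 to 23 per group, and 44 gives about 98 to 99% power

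*Combined protocol and SAP*

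**What the plan says.** Section E names the test and the significance level ("With a one-way ANOVA for 3 groups and alpha set at 0.05") and the assumed rates ("70% of patients for mepivacaine, 35% of patients for hyperbaric bupivacaine, and 25% of patients for isobaric bupivacaine"). It concludes that "the study will require 44 patients per group (N=132) to achieve 80% power to detect a statistically significant difference" among the three groups. It then adds: "Allowing for a 10% dropout and screen failure rate the study will require a total of 144 patients". It gives no standard deviation, effect size, pairwise comparison or multiplicity adjustment.

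The hypothesis at the end of Section A (Specific Aims) is directional and pairwise. Its first part expects that "a greater percentage of patients will ambulate early in the mepivacaine group compared to the two bupivacaine groups". Its second part ranks the two bupivacaine arms against each other, predicting this: "the smallest percentage of patients will ambulate early in the isobaric bupivacaine group".

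**The concern.** A spread from 70% to 25% across three arms is a large effect, and 44 per arm looked like far more than an omnibus test would need for 80% power. If so, the sample-size justification does not support the number it is meant to support, and a reader cannot tell what the trial was sized to show.

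The second issue is what the single 80% figure conceals. It refers to any difference among the three groups, whereas the hypothesis ranks them. A reader could suppose that the hyperbaric-versus-isobaric comparison also has about 80% power, and so take a null result there as evidence of no difference.

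**Working it through.** **Inputs (Section E).** Rates 0.70, 0.35, 0.25; k = 3 equal groups; alpha 0.05; stated n = 44 per group for 80% power. No variance is stated, but for a yes/no endpoint the rates fix or bound it.

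**Between-group spread.** The mean rate is (0.70 + 0.35 + 0.25)/3 = 0.4333. The squared deviations are 0.0711, 0.0069 and 0.0336. Their sum is 0.1117, so the between-group variance is 0.1117/3 = 0.0372.

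**Within-group variance, three choices.**
- Average of p(1−p): (0.2100 + 0.2275 + 0.1875)/3 = 0.2083
- Pooled: 0.4333 × 0.5667 = 0.2456
- Maximum for a binary variable: 0.25

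**ANOVA power.** The effect size is f = √(0.0372/variance). The noncentrality is λ = n × 0.1117/variance, and power comes from the noncentral F distribution with 2 and 3(n−1) degrees of freedom.

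| Variance | f | n per group for 80% | λ at n = 44 | Power at 44 |
|---|---|---|---|---|
| 0.2083 | 0.423 | 20 | 23.6 | 99.4% |
| 0.2456 | 0.389 | 23 | 20.0 | 98.3% |
| 0.25 | 0.386 | 23 | 19.7 | 98.2% |

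The plan's 44 is therefore not reproduced: the total needed is 60 to 69, against the stated 132. Simulating the F test on 0/1 data (400,000 trials) gives power of 79.8% at n = 20, 82.8% at n = 21 and 99.0% at n = 44. A 3×2 chi-square and an ANOVA on the arcsine scale each need 22 per group.

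**Can other inputs rescue 44?**
- Higher target power: 90% needs 25 to 30 per group and 95% needs 30 to 36.
- Larger variance: 80% at n = 44 needs a variance of about 0.498 (f = 0.273), which is impossible because a binary variance cannot exceed 0.25.
- Smaller effect: with the bupivacaine rates held at 35% and 25%, f = 0.273 corresponds to a mepivacaine rate of about 56 to 58%, not 70%.

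**Sensitivity at 44 per group.** With mepivacaine at 65%, 60% or 55%, ANOVA power is 94–97%, 86–90% or 72–78%.

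**Pairwise power at 44 per group** (uncorrected Pearson chi-square, two-sided 0.05, no multiplicity adjustment, exact enumeration):
- mepivacaine vs hyperbaric (70% vs 35%): 91.3%
- mepivacaine vs isobaric (70% vs 25%): 99.2%
- hyperbaric vs isobaric (35% vs 25%): 18.2%; 80% power would need about 329 per group (normal approximation, 328.5 rounded up)

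**Loss allowance.** 132/0.90 = 146.7, so a 10% loss needs 147. A total of 144 allows 12/144 = 8.3%. It is consistent with 44 × 1.10 = 48.4, rounded down to 48 per group. A full 10% loss from 144 leaves 129.6, or about 43 per group. At 43, ANOVA power is 97.9–99.3% and mepivacaine vs hyperbaric has 91%.

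**The case against.** The strongest reply is that 44 came from a pairwise calculation and was only mislabelled as an ANOVA. Several such calculations come close. For 70% vs 35% at 80% power, a Bonferroni alpha of 0.05/3 needs 42 per group, and alpha 0.025 with continuity correction needs 43. At 44 per group, the chance that mepivacaine beats both bupivacaine groups is 81.0% at 0.05/3 each (uncorrected) and 80.4% at 0.025 each (continuity-corrected). That is the first half of the hypothesis, so 44 may suit the trial's real question.

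This is plausible, but the protocol states no such plan. If it is the origin, Section E omits the contrast and alpha that justify the trial's size, and the text still needs correcting.

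A second objection has force: the pairwise figures of 91% and 99% are unadjusted, and the protocol sets out no multiplicity plan. For mepivacaine vs hyperbaric at 44 per group, power falls to 86.8% at 0.025 and 82.0% at 0.05/3, or 75.3% at 0.05/3 with continuity correction. The margin on that comparison thus depends on the adjustment chosen, and the safe direction of the error is established only for the omnibus test.

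It is also fair to say that Section E claims power only for a difference among the three groups. The 18% for hyperbaric vs isobaric is therefore an omission, not part of the arithmetic error. The 8.3% allowance is a rounding matter with negligible effect.

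**Conclusion.** The concern holds. For the test, rates and alpha that Section E names, the required size is 20 to 23 per group, not 44, a discrepancy of about a factor of two. Power at 44 is 98.2–99.4%, not 80%. This rests on the stated rates, equal groups and a binary endpoint, and it holds for every variance choice considered. How 44 was obtained cannot be determined from the document.

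The omnibus test is not underpowered, and nothing here argues for changing enrolment. The practical consequence is that the stated 80% describes neither the named test nor the individual comparisons in the hypothesis. The two mepivacaine comparisons are well powered without adjustment, and mepivacaine vs hyperbaric keeps about 82% at 0.05/3 with an uncorrected chi-square. The predicted ordering of the two bupivacaine groups has only about 18% power. The correction should be made, but it is one of text.

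**What to change.** Keep the target of 144 and revise Section E as follows.

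1. If the calculation behind 44 can be recovered, state its method, contrast, alpha and any continuity correction or multiplicity adjustment. Otherwise, write that under assumed rates of 70/35/25%, 44 per group gives about 98–99% power for the three-group one-way ANOVA at alpha 0.05.
2. Add, labelled as a separate pairwise calculation: at 44 per group, with an unadjusted two-sided 0.05 chi-square test, power is about 91% for mepivacaine vs hyperbaric bupivacaine, 99% for mepivacaine vs isobaric bupivacaine and 18% for hyperbaric vs isobaric bupivacaine. If the pairwise tests are to be adjusted, give the powers at the adjusted alpha as well.
3. Restate the dropout and screen-failure allowance as about 8% (12 of 144).

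The cost is two or three sentences in Section E, with no change to enrolment, design or procedures.
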